[10]. In a retrospective study of 42 adults with DS, not all patients with depression received pharmacotherapy and no patients received a second medication trial if the first was ineffective [10], suggesting under treatment of a generally treatable psychiatric comorbidity.

Under treatment of depression in DS is, in part, related to the lack of data on effective treatment approaches. A review article on depression in DS published in 2011 highlighted that systematic studies on the treatment of depression were critically needed [16]. Even so, now 10 years later, no additional studies have been published and the literature on pharmacotherapy for depression in DS is limited to small case reports and case series [6]. No systematic, prospective studies on the effectiveness, tolerability, and safety of antidepressants in DS have been conducted. Three case series on pharmacotherapy for depression in DS were published more than 20 years ago, prior to the widespread use of modern antidepressants. These three case series reported on the clinical response to tricyclic antidepressants (TCAs) [17–19] and one of these case series also reported on three patients' response to fluoxetine, a selective serotonin reuptake inhibitor (SSRI) [18]. All three patients who received treatment with fluoxetine had a positive response, two of whom had previously failed to respond to TCAs. Of the remaining six patients described in this case series, three other patients responded to TCAs, one responded to a first generation antipsychotic, and two did not receive pharmacologic treatments. Medication side effects are not reported in any of these case series. The significant medical comorbidities and neurocognitive atypicalities associated with DS limit the extent to which our knowledge of the safety and efficacy of antidepressants in the general population can be extrapolated. Our team has collected preliminary data from 11 patients with DS treated with SSRIs for depression which indicate that patients with DS respond to much lower dosages of SSRIs than the general population and may be more sensitive to behavioral side effects at higher dosages [20]. Because of these issues, DS-specific prospective antidepressant trials are needed to inform clinical best practices.

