Data from this study will lay the foundation for the development of evidence-based guidelines for the treatment of depression in DS which will help increase awareness of this comorbidity and promote systematic screening and treatment. Medication treatment strategies for depression used in the general population likely need to be adapted to be safe, tolerable, and effective for adults with DS. Our clinical experience and pilot data suggest that adults with DS may respond to much lower dosages of fluoxetine than are used in the general population and that higher dosages may be associated with intolerable behavioral side effects such as anxiety or behavioral activation [20]. Data from this proposed study will inform best practices for dosing antidepressants in adults with DS. Finally, no specific depression rating

scales have been developed for or validated in DS. Data from this proposed study will inform which existing rating scales can detect depression in DS and which are sensitive to change with treatment. All the rating scales used in this study are in the public domain and therefore can easily be used in clinical practice. The identification of an appropriate rating scale will allow non-psychiatric specialists such as primary care providers as well as psychiatrists with less experience treating adults with developmental disabilities to screen for depression and monitor treatment effects. Overall, the data from this study is expected to improve the accessibility and quality of treatment for depression in DS, a common comorbidity which affects up to 70% of adults with this syndrome

3. General Description of Study Design

[figure not shown]
We are proposing a 16-week, prospective flexibly-dosed, open-label trial of fluoxetine for the treatment of major depressive disorder (MDD) in adults with DS. Participants will be seen at screen, baseline, and following 4, 8, 12, and 16 weeks of treatment. The duration of the trial will allow us to adjust the dose of fluoxetine over the first 12 weeks and allow for stable dosing during the final 4 weeks of the trial. We may complete visits remotely utilizing secure videoconferencing platforms such as Zoom or by phone, as necessary.

*Accommodations for Out of state patients and virtual visits**

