Participants will be monitored for possible pregnancy throughout the study. If a participant is of childbearing potential, a urine pregnancy test will be obtained at Screen. A positive result on a urine pregnancy test will then be confirmed via a blood pregnancy test, and a positive result on a blood pregnancy test will exclude them from study participation. We will continue to assess for pregnancy at all monthly clinic visits by asking participants if they are sexually active and if they are using contraception. Participants of childbearing potential who are sexually active and are not using an approved contraception method will be asked to complete a urine pregnancy test. A positive result on a urine pregnancy test will then be confirmed via a blood pregnancy test, and a positive result on a blood pregnancy test will exclude them from study participation.

Adverse events will be collected via a structured side effect rating scale completed with the participant and their primary caregiver. This will include a list of side-effects that have been reported with fluoxetine at a rate greater than 10% including sexual dysfunction, anorexia, diarrhea, nausea, dry mouth, anxiety, drowsiness, headache, insomnia, yawning, asthenia, tremor, and pharyngitis. Each of these side effects plus any additional complaints will be rated at baseline on a 4-point scale by the caregiver as follows: 0 = none; 1 = mild; 2 = moderate; 3 = severe. This scale is similar to that used by the RUPP Autism Network. Suicidality will be assessed at each visit by directly asking the subject (when verbal skills are sufficient) and the caregiver about any thoughts or behaviors that directly or indirectly might indicate suicidality (e.g., morbid thoughts, self-injury, statements about life being not worth living), when indicated by positive responses. At baseline, if suicidality is endorsed, the Columbia-Suicide Severity Rating Scale (C-SSRS) will be administered per the instructions at www.cssrs.columbia/ed/clinical_trials.html. The C-SSRS will also be administered at each subsequent visit following the first report of suicidality. Subjects and caregivers will also have information on how to contact the on-call physician from our practice group who provides coverage 24 hours/day and 365 days/year. Physicians taking call are familiar with research protocols and can contact the principal investigator at any time.

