All adverse events picked up on the rating scale as new will be recorded by the physician. The physician will also ask about any visits to the doctor, new medication use (e.g. OTC cold medicine), or any other complaints, in order to be confident that most adverse events are uncovered. The physician will keep a running log of adverse events that will record the date of onset, date of resolution, seriousness, severity, and relationship to study intervention (e.g., definite, probable, possible, remote, or none) as well as whether the adverse event led to a change in study intervention or other treatment.

A physician will review vital signs as they become available. All significant adverse events as well as the progress of the study will be reviewed and discussed in detail at the biannual meetings of the Lurie Center Data and Safety Monitoring Board (DSMB). The DSMB includes rotating members of the Lurie Center including pediatricians, pediatric and adult neurologists, pediatric and adult psychiatrists, and independent members outside the Lurie Center.

If at any time during the course of the study, the DSMB judges that the risk to subjects outweighs the potential benefits, the DSMB shall have the discretion and responsibility to recommend that the study be terminated.

Schedule of Measures:

Table 1. Schedule of Measures		Treatment Phase
-------------------------------	--	-----------------

Mass General Brigham Institutional Review Board
Intervention/Interaction Detailed Protocol

Measure	#Screen ^^	#Baseline ^^^	Week 2^	Week 4^^^	Week 6^	Week 8^^^	Week 10^	Week 12^^^	Week 16^^^
Parent Ratings [1]									
Demographics	X								
SCID-5 [2]	X								
MADRS [3]	X	X		X		X		X	X
HAM-D [4] (optional)		X		X		X		X	X
GDS-CS [5]		X		X		X		X	X
PSQI [6]		X							X
Subject Assessments									
Vital Signs, Height, Weight (optional for remote visits)	X								X
Urine Pregnancy Test [7]	X								
Pregnancy Assessment				X		X		X	X
MADRS**	X	X		X		X		X	X
HAM-D** (optional)		X		X		X		X	X
GDS-LD**		X		X		X		X	X
Stanford-Binet-5 (SB-5) or other cognitive assessment	X								
Treating Clinician									
DS Diagnosis [8]	X								
Diagnostic Exam including medical/psychiatric history	X								
Health/Behavior Review	X								
Adverse Effects Review		X	X	X	X	X	X	X	X
CGI-Severity [9]	X	X							X
CGI-Improvement [10]				X		X		X	X
Suicide Assessment [11] / C-SSRS [12]	X	X	X	X	X	X	X	X	X
Concomitant Treatments	X	X	X	X	X	X	X	X	X
Concomitant Medications	X	X	X	X	X	X	X	X	X

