Fluoxetine, an SSRI, has been well tolerated in children, adolescents, and adults. Common adverse reactions (>10%) include, asthenia, nausea, diarrhea, insomnia, nervousness, anxiety, and somnolence. Less common adverse reactions (<10%) include flu symptoms, decreased appetite, dry mouth, dyspepsia, constipation, dizziness, tremor, sweating, fever, vasodilation, flatulence, vomiting, weight loss, decreased libido, abnormal thinking, yawning, rash, pruritis, and abnormal vision. Very rarely, SSRIs may increase the risk of bleeding, a mixed/manic mood episode, suicidal thoughts, and/or QT prolongation. There is also the rare but potential risk of serotonin syndrome. If discontinued abruptly, fluoxetine discontinuation syndrome including flu-like symptoms, insomnia, nausea, balance problems, sensory disturbances, and hyperarousal may occur.

We will assess for these symptoms at all phone, video, and in-person visits. Any side effects will be closely monitored and recorded. In order to manage a side effect or suspected adverse event, the treating clinician is free to delay a scheduled increase or reduce the dose of the study medication. The dose schedules described above are guides only.

Fluoxetine has a half-life of 4 to 6 days. No specific laboratory monitoring is recommended with fluoxetine treatment.

Allergic Reactions

An allergic reaction can occur. Allergic reactions can be mild or serious and can even result in death. Common symptoms of an allergic reaction are rash, itching, skin problems, swelling of the face and throat, or trouble breathing. Participants will be instructed to call the study doctor immediately if they suspect they are having an allergic reaction. Participants will also be instructed to call 911 immediately and get medical assistance if they are having trouble breathing.

Risks to an Embryo or Fetus, or to a Breastfeeding Infant

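### The side-effect scale as described has no prompted item for behavioural activation, which the protocol itself names as possibly intolerable in Down syndrome

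*Combined protocol and SAP*

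**What the plan says.** **Why a trial specific to Down syndrome (DS).** Section 1 reports pilot data from 11 patients suggesting that people with DS "may be more sensitive to behavioral side effects at higher dosages". Section 2 is more specific: "higher dosages may be associated with intolerable behavioral side effects such as anxiety or behavioral activation".

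**What the scale asks.** Section 6 (Safety Monitoring) describes a structured scale completed with the participant and the caregiver. It is to include "a list of side-effects that have been reported with fluoxetine at a rate greater than 10" percent, namely "sexual dysfunction, anorexia, diarrhea, nausea, dry mouth, anxiety, drowsiness, headache, insomnia, yawning, asthenia, tremor, and pharyngitis". On scoring: "Each of these side effects plus any additional complaints will be rated at baseline on a 4-point scale by the caregiver", from 0 (none) to 3 (severe). The physician then records events that appear on the scale as new, and asks about doctor visits, new medicines "or any other complaints, in order to be confident that most adverse events are uncovered".

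**When.** Table 1 schedules the Adverse Effects Review at baseline and at weeks 2, 4, 6, 8, 10, 12 and 16.

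**What Section 7 says.** Under Fluoxetine Treatment: "Common adverse reactions (>10%) include, asthenia, nausea, diarrhea, insomnia, nervousness, anxiety, and somnolence". A second list gives reactions below 10%, and a third gives very rare ones, including mixed or manic episodes. The section adds that these symptoms are assessed at every contact.

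**What is analysed.** Section 9 tabulates the frequency of all side effects and adverse events with 95% confidence intervals. The safety criterion in Section 2 allows no serious or severe drug-related effect. The tolerability criterion is drop-out due to adverse effects below 36%.

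**The concern.** The scale is drawn from effects that are common with fluoxetine generally, while part of the stated reason for the trial is that behavioural effects may differ in DS. Of the two behavioural effects that Section 2 names, anxiety is on the list and activation is not. The list has yawning and pharyngitis, but nothing on restlessness, irritability, agitation or disinhibition.

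Two things follow for the adverse-event table. First, prompted effects and activation would be collected by different methods and then reported side by side as if alike. Second, an unlisted behaviour gets a baseline score only if someone happens to raise it at baseline. Without that score, restlessness present before treatment cannot be separated from restlessness that began on treatment.

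What is at stake is the descriptive safety profile, including the frequency of mild and moderate behavioural effects, and the ability to say that a dose limit or withdrawal was due to activation.

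**Working it through.** **1. The two lists side by side.** The 13 items in Section 6 compare with Section 7 as follows:

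| Section 6 item(s), given as above 10% | Section 7 |
|---|---|
| asthenia, nausea, diarrhea, insomnia, anxiety, drowsiness (6) | above 10% (drowsiness as somnolence) |
| dry mouth, tremor, yawning (3) | below 10% |
| anorexia, sexual dysfunction (2) | nearest entries, decreased appetite and decreased libido, are below 10% |
| headache, pharyngitis (2) | in neither list |

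6 + 3 + 2 + 2 = 13. In the other direction, nervousness is above 10% in Section 7 and absent from Section 6. Activation, agitation, irritability and restlessness are in neither section.

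**2. Routes by which activation could be recorded.** These are the open complaints line on the scale, the physician's open question, and related named symptoms: anxiety and insomnia on the scale, nervousness and manic symptoms in Section 7. None is a prompt for activation, and none ensures a baseline score for it. Section 6 states the 0–3 rating for baseline only. Table 1 implies later ratings, but the text does not say so.

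**3. Direction of error in the frequency table.** With true frequency *f* and capture *s*, the expected recorded frequency is *f × s*. The documents give no value for *s*, so the values here are assumptions. Take *f* = 10% (the frequency used in Section 9) and 20 participants, so that 2 affected are expected. The expected number recorded is 2 × 0.8 = 1.6, 2 × 0.65 = 1.3 or 2 × 0.5 = 1.0. The missing baseline rating can push the other way, by letting pre-existing behaviour be logged as new. The net direction is therefore unknown.

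**4. The safety figure.** Section 9 states an 85% or greater chance of seeing a serious or severe event of 10% frequency, with n = 18.
- As stated: 1 − 0.9^18 = 0.850. It reproduces.
- The formula treats every event that occurs as recorded. With capture *s* it becomes 1 − (1 − 0.10*s*)^18.
- At an assumed *s* = 0.9: 1 − 0.91^18 = 0.817.

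**5. The tolerability figures.** Section 9 assumes 85% of 20 = 17 evaluable participants. Drop-out below 36% means at most 6 of 17.
- True intolerance 20%: P(X ≤ 6) = 0.962 (stated above 90%). It reproduces.
- True intolerance 50%: P(X ≥ 7) = 0.834 (stated at least 80%). It reproduces.
- Suppose that 10% of all adverse-effect drop-outs were put down to another cause. The analysis plan takes those who withdraw for other reasons out of the denominator, and the 0.834 becomes 0.804. If they stayed in the denominator it would be 0.710.
- Activation is only one cause of such drop-outs, so a 10% error across all of them would need a larger failure for activation itself.

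**The case against.** The strongest reply has four parts.

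- **The list is not stated to be complete.** The form is not among the documents, and it holds more than the 13 effects: a note to Table 1 places the suicide assessment within the same review. An activation item may already exist.
- **Related symptoms are covered.** Anxiety and insomnia are on the scale. Section 7 brings nervousness and manic symptoms into the enquiry at every contact.
- **Capture does not rest on the caregiver volunteering a complaint.** The participant contributes, additional complaints are scored, and a physician asks directly about anything else. Activation bad enough to be intolerable should also surface in dose decisions, which Section 6 bases partly on tolerability.
- **The aims do not turn on the checklist.** They depend on serious or severe related events and on drop-out due to adverse effects.

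Most of this stands, and it confines the point to the frequency table and to attribution. It does not remove the point: nothing in the documents gives activation a named prompt or a planned baseline score. If the form already has such an item, the protocol should say so.

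A reader might also infer that the plan fails to test whether behavioural effects rise with dose. No aim sets out to test that. Section 2's remark on higher doses is rationale, and Aim 3 only estimates mean dose.

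**Conclusion.** The gap is real and modest. The scale as described prompts for one of the two behavioural effects that Section 2 names and not the other. The tabulated frequency of activation would be less reliable than those of the prompted effects and should not be compared with them. The documents do not allow the size of that error to be fixed.

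The effect on the formal criteria is probably small. The 85% falls to about 82% at an assumed 90% capture. That level is a judgement that serious or severe events are rarely missed, not a figure from the documents. For drop-out, 0.834 falls to 0.804 under the planned denominator at an assumed 10% misattribution, still above the stated 80%.

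Three stronger readings are tempting and not supported:
- **That the trial could call fluoxetine safe and tolerable because activation was never asked about.** Open enquiry, related items and criteria based on severe events and drop-out make this unlikely.
- **That the protocol expects activation to limit treatment.** Section 2 says only that it may occur, and Section 1 expects the drug to be safe and well tolerated.
- **That the 85% falls to 78%, 70% or 60%.** Those values follow from assumed capture of 80%, 65% and 50%. Capture that low is more plausible for mild or moderate events, which the 85% does not describe.

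**What to change.** 1. In Section 6 (Safety Monitoring), add prompted items for activation, for example restlessness, irritability or agitation, and impulsivity or disinhibition, together with nervousness.
2. State there that all items are rated 0–3 at baseline and at every later Adverse Effects Review, so that new or worsened effects are judged against a recorded starting point.
3. Reconcile the above-10% lists in Sections 6 and 7 (nervousness, dry mouth, tremor and yawning at least).

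Optionally, add a listing of behavioural events with the dose at onset, using the onset dates already logged. It should be labelled descriptive: under flexible titration, dose is confounded with time on treatment and with tolerance.

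The cost is a few lines on an existing form and a short protocol edit. The downside is that prompting will raise the reported frequency of mild behavioural events. The report should say that these items were prompted, and the baseline ratings help to interpret the rise.

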Depression is a common psychiatric comorbidity with a lifetime prevalence of 16.6% in the United States [25]. Adults with DS have a four- to five-times increased risk of developing depression compared to the general population [13], suggesting that up to 70% of individuals with DS may experience depression in their lifetime. Compared to other known comorbidities associated with DS such as obstructive sleep apnea, congenital heart defects, blood cancers, and cataracts, depression is both relatively more highly prevalent and understudied. No reports on the use of modern antidepressants in DS have been published in the past more than 25 years. Our knowledge of the safety and efficacy of antidepressants in the general population may not be applicable to patients with DS because of the associated medical comorbidities and neurocognitive differences.

The central hypothesis of this project is that adults with major depression and DS will experience an improvement in depressive symptoms after a course of fluoxetine treatment. We also expect that fluoxetine will be safe and well tolerated. This study will provide much needed preliminary prospective

data regarding the effectiveness and tolerability of fluoxetine for these symptoms in DS and is a necessary first step prior to conducting a larger, more definitive placebo-controlled trial.

2. Specific Aims and Objectives

Specific Aim 1: Determine whether a 16-week prospective, open-label trial of fluoxetine shows preliminary evidence of effectiveness, safety, and tolerability in adults with DS and major depressive disorder (MDD).

This aim addresses our central hypothesis that fluoxetine will be effective and safe in the treatment of depression in adults with DS.

- A)** For preliminary evidence of effectiveness, we will require an observed response rate (where response is defined as a 16-week CGI-I rating of “much improved” or “very much improved”) of 35% or greater. We will use the CGI-I rather than a depression scale for our effectiveness criterion because of the absence of existing data supporting the usefulness of common scales for quantifying depression severity in adults with DS.
- B)** For preliminary evidence of safety, we will require no observation of serious or severe adverse effects possibly, probably, or definitely associated with fluoxetine.
- C)** For preliminary evidence of tolerability, we will require an observed drop-out rate due to adverse effects less than 36%.

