We will estimate percentage response to fluoxetine treatment, and corresponding 95% confidence interval, for adults with DS using the proportion of participants with CGI-I scores ≤ 2 at 16 weeks. Participants with missing 16-week CGI-I scores will be treated as non-responders. Frequency of all side effects and adverse events and corresponding 95% confidence intervals will be tabulated. Percent tolerating treatment and corresponding 95% confidence intervals will be estimated using the proportion of participants who did not withdraw from the study before 16 weeks due to reasons other than side effects or an adverse event who discontinue treatment due to side effects or an adverse event. We will also use the 16-week study retention rate and corresponding 95% confidence interval, calculated as the proportion of the participants enrolling in the study who remain in the study for 16 weeks, as a measure of feasibility.

To estimate changes in depression scale scores, including the MADRS, HAM-D, GDS-LD, and GDS-CS, we will use repeated measures linear regression models, as implemented in PROC MIXED in SAS and fit using REML estimation, with repeated measurements of clinical scores as outcomes and time, in categories, as the predictor. We will allow unstructured covariance between repeated measurements from the same participant. Our primary interest will be only in the difference between baseline and week 16 scores, but all observed scores will be included as outcomes, given that partially observed scores may be informative for estimation. We will obtain an estimate of 16-week change and corresponding 95% confidence interval using a contrast of the week 16 and baseline model parameters. Sensitivity to change will be compared between scales using standardized effect sizes, calculated using the model-estimated 16-week change in each outcome divided by 1) the model-estimated standard deviation of the outcome at baseline and 2) the model-estimated standard deviation of the change score. Spearman correlations will quantify the strength of association between change in depression scale score and CGI-I ratings among those with observed 16-week data. We will also tabulate and compare the percent of item-level missing data for each scale.

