The electronic database used to house these data until analyses are needed will be a web-based electronic data capture program created uniquely for this project. The database will be password protected and only certain users will be given access to the web-based program. This will protect the electronic data against any unauthorized persons from entering the dataset and jeopardizing the integrity of the data or engaging in some sort of malicious piracy.

As this project matures into the data analysis stage, data will be queried and exported to statistical software for data analysis.

Safety Monitoring

A physician will monitor adverse effects at each visit. In addition, he or she will review vital signs and laboratory data, as they become available. All of these values are recorded and then reviewed continuously by the PI. All AEs that arise are recorded by a physician. This includes documenting the date of onset, duration, severity, seriousness, and relationship to study medication. Any severe or serious AEs will be reported as soon as possible to the PI. All significant AEs as well as the progress of the study will be reviewed and discussed in detail at the biannual meetings of the Lurie Center Data and Safety Monitoring Board (DSMB). The Lurie Center DSMB includes rotating members of the Lurie Center including pediatricians, pediatric neurologists, child and adolescent psychiatrists specializing in developmental disabilities. All serious or unexpected AEs that are possibly related to drug treatment will be reported to the Partner's IRB within 3 working days from notification of the event. Examples of serious AEs include: death, life-threatening event, inpatient hospitalization, persistent or significant disability/incapacity, congenital anomaly/birth defect, and events that require medical or surgical intervention to prevent death, disability, or hospitalization. An unexpected AE is one that is not described in the protocol. Any serious or unexpected AE that is possibly related to fluoxetine will be reported to the IRB according to the reporting guidelines. Any action resulting in temporary or permanent suspension of the study will also be reported to our IRB.

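### The adverse event log is triggered by checklist items that are new, and nothing says that worsening over the baseline grade counts, so severe worsening can go unlogged

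*Combined protocol and SAP*

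**What the plan says.** Section 6, Safety Monitoring, collects adverse events with a structured checklist of effects reported with fluoxetine at a rate above 10%. Among them are anorexia, anxiety, drowsiness, insomnia and asthenia. On grading it says: "Each of these side effects plus any additional complaints will be rated at baseline on a 4-point scale by the caregiver as follows", with 0 for none and 3 for severe. The link from checklist to log is: "All adverse events picked up on the rating scale as new will be recorded by the physician". A further inquiry follows: "The physician will also ask about any visits to the doctor, new medication use (e.g. OTC cold medicine), or any other complaints". The physician's log holds onset, resolution, seriousness, severity and relationship to the intervention. Table 1 schedules an Adverse Effects Review at baseline and at every later visit.

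Two other sections describe recording without the word new. Section 7 (Fluoxetine Treatment) says: "Any side effects will be closely monitored and recorded". Section 10 (Safety Monitoring) says: "A physician will monitor adverse effects at each visit", and "All AEs that arise are recorded by a physician".

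Two results depend on what is recorded. For preliminary evidence of safety, Aim 1B in Section 2 states: "we will require no observation of serious or severe adverse effects possibly, probably, or definitely associated with fluoxetine". The Statistical Analysis Plan in Section 9 states: "Frequency of all side effects and adverse events and corresponding 95% confidence intervals will be tabulated".

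**The concern.** A baseline grade is taken for every item, but the protocol does not say how a later grade is to be compared with it. On an ordinary reading, insomnia that moves from mild (1) at baseline to severe (3) on fluoxetine is not a new item.

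This is a realistic case in this population. Entry requires major depressive disorder with a MADRS score of at least 20. Section 1 lists reduced appetite and low energy among the features of depression in Down syndrome, and these overlap with the checklist items anorexia and asthenia. Section 7 names asthenia, insomnia, anxiety and somnolence as common reactions to fluoxetine. The closing paragraphs of Section 2 name anxiety and behavioral activation as side effects that the investigators think may occur at higher doses. Some of the effects the study most needs to see may therefore appear as worsening of something already present.

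At stake are the Aim 1B conclusion, which a single related severe effect reverses, and the adverse event frequencies. An unlogged worsening moves both in the same direction, toward apparent safety.

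**Working it through.** **1. What each recording rule says about worsening**

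| Place | What is recorded | Is worsening over baseline covered? |
|---|---|---|
| Section 6, checklist rule | Checklist items that are new | Not stated; not on an ordinary reading |
| Section 6, further inquiry | Doctor visits, new medication, other complaints | Not stated; most naturally complaints outside the checklist |
| Section 7 | Any side effects | Not stated; wide enough to include it |
| Section 10 | All adverse events that arise | Not stated; depends on what counts as an adverse event |

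No section defines a treatment-emergent event. The 0 to 3 grading is stated for baseline only. The protocol also does not say whether the caregiver's grade 3 is what Aim 1B means by severe. Two physicians could handle the same 1-to-3 change differently, and both could point to the protocol.

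**2. The plan's own detection figure**

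Inputs from Section 9, Sample Size Considerations: true frequency of a serious or severe associated event 10%; 18 participants followed long enough (90% of 20); stated chance of observing at least one, 85% or greater.

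P(at least one) = 1 − (1 − 0.10)^18 = 1 − 0.9^18 = 0.850. The stated figure is reproduced. It assumes that every qualifying event is recorded.

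**3. Illustration of incomplete logging**

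Let m be the share of qualifying events that are not logged. The documents give no value for m, so the range is an assumption. The logged rate is 0.10 × (1 − m), and detection is 1 − (1 − 0.10 × (1 − m))^18.

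| m (assumed) | Logged rate | Chance of at least one logged event, n = 18 |
|---|---|---|
| 0% | 10% | 85.0% |
| 10% | 9% | 81.7% |
| 20% | 8% | 77.7% |
| 30% | 7% | 72.9% |
| 50% | 5% | 60.3% |

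**4. The same loss expressed as a true rate**

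The logged rate that gives 85% detection is 1 − 0.15^(1/18) = 0.100. The true rate needed is 0.100 / (1 − m): 12.5% when m = 20%, and 20% when m = 50%.

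Detection falls as m rises at every value, so the direction of the effect does not depend on the assumed shares. Its size does.

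**The case against.** A reader might infer that the protocol logs nothing except new checklist items, so that worsening is excluded by rule. The documents do not support that. The Section 6 sentence says new items will be recorded; it does not say that other items will not. The same paragraph adds an open inquiry, Section 7 speaks of recording any side effects, and Section 10 has a physician monitor adverse effects at each visit. A graded baseline would also have little purpose if only presence or absence mattered, so new can be read as new relative to the baseline grade.

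The exposure is also narrower than all serious or severe events. Section 10 gives serious events their own reporting route to the IRB. A worsening that leads to withdrawal for side effects would enter the tolerability estimate. Aim 1B turns on observing an event, and its text does not refer to the checklist trigger. Finally, the unlogged shares above are assumptions, and each treats that share as wholly missed despite the other routes.

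These points stand, and they limit the claim. They do not remove it. None of the broader statements says that worsening counts. The sentence in Section 10 about events that arise can itself be read as referring to onset. The route that connects the checklist to the log still carries the narrower trigger. A favorable reading of new is available, but the protocol does not require it.

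**Conclusion.** The point holds as a problem of an undefined trigger and inconsistent recording rules, not as a stated exclusion of worsening. A physician who follows the Section 6 wording literally can leave out a non-serious but severe worsening of a symptom present at baseline. That omission would favor the drug in the adverse event tables and in the Aim 1B rule.

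A reader might take the fall from 85% to between 60% and 82% as the plan's actual loss. It is not. It illustrates assumed unlogged shares of 10% to 50%, applied to the plan's own case of a 10% event in 18 participants. The documents establish the direction but not the size. Because one related severe effect decides Aim 1B and the repair is cheap, the change should be made.

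**What to change.** - In Section 6, change the trigger so that a checklist item is recorded when it is new or graded worse than that participant's baseline grade.
- State that the full checklist is re-graded 0 to 3 at every Adverse Effects Review in Table 1 and compared with baseline.
- For each such event, log the on-treatment severity and the physician's relatedness rating.
- State whether a checklist grade of 3 counts as severe for Aim 1B.
- Align the recording statements in Sections 6, 7 and 10 to this one definition, and use it for the Section 9 tables.

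The cost is a few sentences and a baseline comparison on an existing form; the baseline grades are already planned. The downside is more logged events, some of which will be fluctuation of the depression itself. The relatedness field already in the log can help separate these.
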